1.0 Background

Bone fractures are a widespread and costly problem (1). A meta analysis of clinical studies concluded that people with type 2 diabetes mellitus (T2D) are at a higher-than-expected risk of a hip fracture than those who do not have the disease (2). Costs associated with treating osteoporotic fractures alone exceed \$17.5 billion annually in the US (3), and the elderly who sustain a hip fracture are 4.6 (men) and 2.8 (women) times more likely to die within a year (4). Despite the economic burden to society and poor quality of life that fractures impose, the cause for the disproportionate increase in fracture risk with aging and T2D is unknown.

Beyond bone strength and aBMD to assess fracture risk

Traditionally, osteoporosis is viewed as a problem of low bone density causing reduced bone strength. However, there is a well-known disproportionate increase in fracture risk relative to the age-related decrease in bone density (5-8), which is commonly attributed to certain limitations in the clinical measurement of aBMD. Namely, DXA is a projection method that does not discern the relative contribution of macro-structure, micro-architecture, collagen integrity, or porosity to fracture resistance. This is one reason why the NIH held a conference on bone quality defining it as “the sum total of characteristics of the bone that influence the *bone’s resistance to fracture*” (9) and the reason why the World Health Organization developed FRAX, an on-line fracture risk calculator using risk factors as input (10). To date, there is no definitive bone quality measurement that improves the assessment of fracture risk, and FRAX still underestimates risk for certain prevalent diseases like diabetes (11). Thus, **what would be useful to improving clinical care is a diagnostic assessment that actually relates to the mechanism by which aging and diabetes lowers fracture resistance.**

Reference Point Indentation (RPI) measurements

discriminate fracture patients from non-fracture patients

In a hospital in Barcelona, RPI was performed using the BioDent instrument on the tibia mid-shaft of 27 women (79.1 ± 7.8 years) recovering from an osteoporotic fracture and 8 controls with a similar age range (83.2 ± 5.3 years) (12). The indentation distance increase (IDI) for the fracture patients was 47% greater (i.e., more susceptible to damage formation) than for the non-fracture patients (p=0.008). In a follow-up study, the same research team performed similar RPI tests for 4 groups of patients: 20 with no history of a fracture

[figure not shown]

Fig. 1: The bone micro-anatomy gives rise 3 T_2 components when analyzed by ^1H NMR spectroscopy. One of these components, bound water correlates with the fracture toughness (K_{1c}) of bone.

or bisphosphonate (BP) use, 38 with typical hip fractures, 6 with atypical fractures (below lesser trochanter), and 6 on BP for 5 to 12 years (but no fracture). Total indentation distance (TID) and IDI were significantly higher (worse) for the fracture cases than for the non-fracture cases (no difference between typical and atypical). The proposed project aims to assess a new, hand-held RPI instrument (OsteoProbe) for its ability to discriminate osteoporotic bone from normal bone in comparison to the clinical gold standard DXA. Although the bone measurement from OsteoProbe at the tibia mid-shaft was found to be different between women with and without type 2 diabetes (13), there is currently no evidence that it is any better than DXA in predicting fracture risk.

Other New Assessment Tools for Fracture Resistance Assessment

Current efforts in the labs of the Co-PI [name] and his collaborators to improve fracture prediction include Raman spectroscopy (RS) (14-15), **(NMR) relaxometry** (i.e., quantitative, sub-voxel MRI) (16-17), and **reference point indentation (RPI)**. All these techniques can potentially be translated to the clinical assessment of bone, but NMR/MRI (18,19) and RPI (12,20) are closest to providing clinically useful information about bones. Moreover, the NMR technique can be combined with other MRI approaches that provide structural and architectural parameters of bone (21).

After establishing the biophysical origins of proton signals within human cortical bone using NMR relaxometry (Fig. 1) (17), we reported that bound water can explain the age-related decrease in the material strength of human cortical bone ($r^2=62\%$, $p<0.001$) (22) and that loosely bound water detected by NMR contributes to bone toughness (16). Perhaps more relevant to diabetes and aging effects on bone, we found that bound water also correlates with the ability of bone to resist crack propagation (Fig. 1). We hypothesize that increasing pore water (intra-cortical porosity) and decreasing bound water (surrogate of 'matrix quality') makes bone susceptible to fracture.

BioDent-RPI is a relatively new analytical technique that provides properties related to the ability of tissue to resist micro-indentation (a micron-size probe tip penetrates bone tissue over 10-20 cycles in force control). As such, the best way to quantify resistance to indentation is still an unresolved issue, and differences in RPI properties are likely context or disease dependent. Thus, we performed a series of experiments to show that RPI i) is sensitive to bone tissue organization (anisotropy), ii) provides significant correlations, albeit weak, with apparent bone fracture toughness ($r^2=24\%$, $p<0.05$), and iii) resistance to indentation decreases with age (manuscript under review). We hypothesize that low resistance to indentation is indicative of fragile bone.

Innovation

The proposed studies are based on i) *novel view* that water, collagen, and damage are important to fracture resistance, ii) *state-of-the-art* analysis tools that go beyond bone mass to quantify properties of the matrix, and iii) *unique* access to patients with clear differences in fracture resistance through an orthopaedic clinical at VUMC that fixes 100 distal radius fractures per year. These studies have the potential to i) *shift the paradigm* of bone health to one that includes characteristics of the bone matrix and its contribution to microdamage resistance, and ii) *transform* the manner in which clinical diagnostic methods for bone health are developed, from solely X-ray based to include MRI-based and mechanical characterization tools.

2.0 Rationale and Specific Aims

The goal of this study is to determine whether two new, non-X-ray techniques can discriminate between high-energy fractures of normal bone (trauma) and low-energy fractures (fragility) of osteoporotic bone. The current gold-standard for assessing fracture risk – areal bone mineral density (aBMD) by dual energy X-ray absorptiometry (DXA) – is not particularly effective at identifying individuals who are at risk of suffering a fracture (5, 23-25). Yet, there is a growing population of diabetics and elderly individuals prone to fractures (6, 26-28). In effect, the age-related and diabetes-related increase in fracture risk is independent of a person's aBMD (6, 7, 29, 30). These findings stress the urgency in developing diagnostic tools that can improve fracture risk prediction so that patients can be treated with the appropriate anti-fracture therapies.

Shifting from the current paradigm of using X-ray based modalities to assess fracture risk, the reference point indentation (RPI) method acquires direct measurements of 'material quality' of the bone tissue (31), while magnetic resonance imaging (MRI) assesses bound water and pore water concentrations that relate to the material properties of cortical bone (18,22). Specifically, the OsteoProbe-RPI engages the patient's bone, and upon applying an impact force, it measures the ability of the tissue to resist micro-indentation. Recently, this measurement – currently known as bone material strength (BMS) – was found to be lower in post-menopausal women with type 2 diabetes than age-matched women without diabetes (13). Our novel MRI methods utilize relaxation-selective preparations with ultra-short echo-time (UTE) acquisition to separately measuring bound and pore water concentrations on bone (19), which we postulate to reflect matrix quality and porosity (16). Despite the encouraging results from studies applying RPI and UTE-MRI to bone, there is no evidence that *a local measurement of bone material quality or bulk measurements of bound and pore water are predictive of fracture resistance at sites that are prone to fragility fractures.*

By affirming the ability of these tools to discriminate a fragility (osteoporotic) fracture from high-energy (trauma) fracture, the proposed study will provide justification for large prospective studies that i) evaluate the ability of these techniques to predict fracture, ii) assess whether these techniques are informative on how drug therapy is affecting bone, and iii) whether intra-operative RPI is useful to surgical guidance (e.g., placement of bone screws).

AIM 1: DETERMINE WHETHER INDENTATION RESISTANCE IS DIFFERENT BETWEEN PATIENTS WITH FRAGILITY FRACTURES AND THOSE WITH HIGH ENERGY FRACTURES.

Hypothesis: Local indentation resistance (BMS) of the distal one-third radius is lower for patients with a fragility wrist fracture than healthy patients with a traumatic wrist fracture.

Approach: Men and women (>18 y.o.) undergoing surgery to fix a distal radius fracture involving the metaphysis will be recruited into the study. Exclusion criteria will include known risk factors of pathological fractures (e.g., bone metastasis) and long-term or recent treatment for osteoporosis (e.g., bisphosphonate). In addition to standard-of-care, the orthopaedic surgeon will indent the cortex between the one-third distal radius (10-15 sites separated by 2 mm) and the ultradistal (UD) site with the OsteoProbe prior to stabilizing the fracture with a volar plate. The patient's arm will be secured to prevent rotation of the bone. Postoperatively, the patient's hips, spine, and contra-lateral radius will be imaged by DXA to determine aBMD following standard protocols at the Vanderbilt Clinical Research

Center (CRC). Patients will be stratified into two groups: high-energy fracture (e.g., motor vehicle crash) of *normal bone* and low-energy fracture (e.g., fall from a chair or standing height) of *osteoporotic bone*. We expect BMS to be less for the fragility fractures than for non-osteoporotic fractures. In addition, the lower BMS for the fragility fracture group will be significant when including aBMD, age, and body mass index (BMI) as covariates.

AIM 2: DETERMINE WHETHER BOUND WATER AND PORE WATER ARE DIFFERENT BETWEEN PATIENTS WITH FRAGILITY FRACTURES THAN THOSE WITH HIGH ENERGY FRACTURES.

Hypothesis: Bulk bound and pore water of the distal one-third radius will be lower and higher, respectively, for patients with fragility wrist fractures than healthy patients with a traumatic wrist fracture.

Approach: Postoperatively, patients in Aim 1 may also have their contralateral arm (distal one-third) imaged by our unique UTE-MRI technique (Philips Achieva 3T scanner) using wrist coil at the VUIIS. By including reference markers in the scan, the average concentration of bound water and pore water (mol ¹H per bone volume) will be quantified for a 14 mm axial segment (0.5 mm in-plane resolution). We will also image age-matched and gender-matched individuals without a history of fractures to the operative fracture patient group. We expect the fragility fracture patients to have significantly less bound water and more pore water than high-energy fracture patients and non-fracture patients, and this difference will be significant after adjusting for aBMD and BMI. In addition, bound water will be less and pore water more for the elderly fragility fracture group than for the elderly non-fracture group (also adjusting for aBMD). A group of non-operative distal radius fracture patients will also be recruited to undergo a DXA scan at the CRC and some of those patients will be asked to undergo an MRI scan at VUIIS.

3.0 Animal Studies and Previous Human Studies

PRELIMINARY STUDIES

Since we were able to successfully apply the BioDent-RPI instrument to human cortical bone, we became intrigued about the possibility of using the newer RPI instrument from Active Life Scientific, Inc., known as the OsteoProbe®. Unlike the BioDent® that indents the bone over 10 to 20 cycles at a target force of 10 N, the OsteoProbe-RPI indents the bone with one impact load reaching a target force of 40-45 N (31) and recording the indentation depth. The probe tip geometry of the micro-indenter is the same between the BioDent and the OsteoProbe, but the higher force generated by the OsteoProbe causes greater wear of the tip. Therefore, indentation depth into bone is normalized by the indentation depth into a reference block of plastic, thereby accounting for any subtle changes in tip surface geometry. The inventors called this ratio bone material strength (BMS), although this normalized indentation depth or Index is not necessarily a measure of strength. The misnomer aside, the OsteoProbe has the advantage of being a hand-held instrument. As long as the OsteoProbe tip is normal to the bone surface ($\pm 10^\circ$), there is enough internal spring force to properly trigger the impact force. In effect, an orthopaedic surgeon who has exposed a bone during surgery can use the OsteoProbe intra-operatively.

To examine the feasibility of indenting a patient's bone with the OsteoProbe, we hypothesized that BMS differs between the thicker, less porous tibia mid-shaft and the thinner, more porous forearm bones (proximal humerus and distal radius), but that the measurements at the tibia correlate with those acquired from forearm bones. Distal radius, tibia mid-shaft, and proximal humerus (left and right side) were acquired from 10 cadavers (half males and half females; 78 yo to 98 yo). While keeping the bones moist with phosphate buffered saline, 8 indents were performed in a row (~3 mm spacing) using the OsteoProbe-RPI (Fig. 2). BMS was the depth of the indent divided by the mean indentation depth into a

PMMA standard (performed 8 times with each new tip and each donor). To determine whether BMS varied along the length of the bone, each BMS value per bone was normalized to the mean BMS among the 8 indents for each donor, and then these relative BMS values were plotted as a function of location of the indent (Fig. 2). In doing so, BMS increased moving from the thinner metaphysis (distal) to the thicker diaphysis portion (proximal) of the radius. *We will indent the cortex between the one-third distal radius (10-15 sites separated by 2 mm) and the ultradistal (UD) site.* Even though BMS varied among the anatomical locations but not between the left and right side (Fig. 3), tibia BMS directly correlated with proximal humerus BMS (avg of 8: $r=0.69$, $p=0.027$). Tibia BMS and distal radius BMS did not correlate ($p=0.19$). *We will indent distal radius before fracture fixation to determine whether BMS differs between fragility fracture and high-energy fracture cases.* Interestingly, BMS correlated with intra-cortical porosity as determined by high-resolution, micro-computed tomography (6 μm), especially for the distal radius (Fig. 4). This raises the intriguing possibility that the OsteoProbe-RPI is sensitive to micro-structure and tissue quality, two determinants of fracture resistance. Even though some of the bones had a thin cortex, the indent did not punch through the cortex (Fig. 4).

To translate and evaluate an *in-vivo* MRI protocol for

[figure not shown]

Fig. 3. Indentation resistance (bone material strength) increased from thinner metaphysis to thicker diaphysis of the distal radius. BMS varied among the different bones.

[figure not shown]

Fig. 4. μCT images of the indent and pores for the thick cortex of the tibia med-shaft (above) and thin cortex of the radius (middle). BMS is negatively related to porosity.

[figure not shown]

Fig. 2. Location of indents for each cadaveric bone as performed by the hand-held OsteoProbe-RPI (Right).

quantitative mapping of bound and pore water concentrations in cortical bone, UTE imaging sequences (19) were implemented on a clinical 3T scanner. Images of the lower leg and wrist were acquired on three subjects (mean age 33, M/F 1/2) to generate bound and pore water concentration maps of the tibia and radius (Fig. 5). Inter-scan variability in bound water maps ranged from 3-13% (mean 7%) in the tibia and 1-23 % (mean 10%) in the radius. Pore water maps showed inter-scan variability ranging from 5-18% (mean 10%) in the tibia and 8-27% (mean 17%) in the radius. With the addition of a new wrist coil for the 3T scanner, we anticipate a reduction in inter-scan variability by 2-4x.

4.0 Inclusion/Exclusion Criteria

Inclusion/exclusion criteria for patients with a high-energy or fragility fracture requiring operative fixation (Arm 1)

Number of patients in Arm#1= 60 patients

Inclusion criteria:

1. Patients who are 18 years of age or older. This age range accounts for 60% of all distal radius fractures seen at Vanderbilt University Medical Center.
2. Patients who have sustained a low or high energy distal radius fracture that involves the metaphysis and requires open reduction internal fixation using volar plating.
3. English speaking due to feasibility of employing study personnel to deliver and assess study intervention.

Exclusion criteria:

1. Patients who have known risk factors of pathologic fractures (e.g. bone metastasis)
2. Patients who have received treatment for osteoporosis (e.g. bisphosphonate) within the last 5 years or whose treatment lasted longer than 5 years
3. Patients who have Type 1 diabetes
4. Patients who have other bone disease (e.g., osteogenesis imperfecta, Paget's disease, thyroid disease, Vitamin D deficiency, hyperparathyroidism)
5. Patients that have a history of cancer, abnormal serum calcium, or chronic steroid use
6. Patients that would not be able to have a DXA scan (weight >350lbs, hardware in hips, patients that have lap band device)
7. Patients who are pregnant or who think they may be pregnant
8. Patients that have a medical contraindication to MRI (if patients are undergoing a study MRI)
9. Patients who have concurrent, bilateral upper extremity fractures where hardware or casting may affect study scan measurements
10. Patients who have distal radial shaft fractures

Exclusion criteria 1-5 are included because the goal of the study is to demonstrate whether new bone measurements differentiate normal bone from fragile bone. These exclusion criteria eliminate confounding factors that affect fracture resistance of bone in ways that are independent of osteoporosis. Exclusion criteria 6-8 are practical since DXA/MRI scans cannot accommodate all people.

Inclusion/exclusion criteria for patients with no fracture (Arm 2)

Number of patients in Arm#2= 40 patients

Inclusion criteria:

1. Patients who are 18 years of age or older.
2. Patients who have no history of fracture or family history of pathologic fracture
3. English speaking due to feasibility of employing study personnel to deliver and assess study intervention.

Exclusion criteria:

1. Patients who have received treatment for osteoporosis (e.g. bisphosphonate) within the last 5 years or whose treatment lasted longer than 5 years
2. Patients who have Type 1 diabetes
3. Patients who have other bone disease (e.g., osteogenesis imperfecta, Paget's disease, thyroid disease, Vitamin D deficiency, hyperparathyroidism).
4. Patients that have a history of cancer, abnormal serum calcium, or chronic steroid use.
5. Patients that would not be able to have a DXA scan (weight >350lbs, hardware in hips, patients that have lap band device)
6. Patients who are pregnant or who think they may be pregnant.
7. Patients that have a medical contraindication to MRI.

Exclusion criteria 1-5 are included because the goal of the study is to demonstrate whether new bone measurements differentiate normal bone from fragile bone. These exclusion criteria eliminate confounding factors that affect fracture resistance of bone in ways that are independent of osteoporosis. Exclusion criteria 6- 8 are practical since DXA/MRI scans cannot accommodate all people.

Inclusion/exclusion criteria for patients with a high-energy or fragility fracture requiring nonoperative treatment (Arm 3)

Number of patients in Arm#3= up to 10 patients

Inclusion criteria:

1. Patients who are 18 years of age or older. This age range accounts for 60% of all distal radius fractures seen at Vanderbilt University Medical Center.
2. Patients who have sustained a low or high energy distal radius fracture that requires nonoperative treatment
3. English speaking due to feasibility of employing study personnel to deliver and assess study intervention.

Exclusion criteria:

1. Patients who have known risk factors of pathologic fractures (e.g. bone metastasis)
2. Patients who have received treatment for osteoporosis (e.g. bisphosphonate) within the last 5 years or whose treatment lasted longer than 5 years
3. Patients who have Type 1 diabetes
4. Patients who have other bone disease (e.g., osteogenesis imperfecta, Paget's disease, thyroid disease, Vitamin D deficiency, hyperparathyroidism)
5. Patients that have a history of cancer, abnormal serum calcium, or chronic steroid use
6. Patients that would not be able to have a DXA scan (weight >350lbs, hardware in hips, patients that have lap band device)
7. Patients who are pregnant or who think they may be pregnant

8. Patients that have a medical contraindication to MRI (if patients are undergoing a study MRI)
9. Patients who have concurrent, bilateral upper extremity fractures where hardware or casting may affect study scan measurements

Exclusion criteria 1-5 are included because the goal of the study is to demonstrate whether new bone measurements differentiate normal bone from fragile bone. These exclusion criteria eliminate confounding factors that affect fracture resistance of bone in ways that are independent of osteoporosis. Exclusion criteria 6-8 are practical since DXA/MRI scans cannot accommodate all people.

This study will proceed until all eligible patients have been enrolled and have completed their follow-up.

Randomization

There is no randomization aspect to this study.

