10.0 Statistical Considerations

Data will be analyzed using the statistical software package Stata (version 11.0, College Station, TX) with the assistance of [name], Biostatistician III. Statistical comparisons will be performed using two-sided tests at the 5% significance level. Mann-Whitney test will assess whether differences in properties between groups are statistically significant. Next, general linear models (GLMs) will be used to determine whether the case explains each property after adjusting for aBMD (or T-score), BMI, and age. Using a robust analysis with GLMs, the data will be bootstrap with 500 replicates. Based on the variance from our cadaver studies and expected mean BMS for 'normal' bone as measured by Farr et al. (32), a sample size of 15 per group will provide 87% power to detect a 11.2% difference between the 2 cases at an α of 0.05. With 60 participants (15 per variable) will allow us to determine whether fracture type significantly explains BMS after adjusting for 3 covariates (aBMD, BMI, age). Note that there will be overlap in the participants between Aim 1 and Aim 2. From our limited imaging studies, we can expect bound and pore water of normal bone to be 22 mol $^1\text{H}/\text{L}$ and 10 mol $^1\text{H}/\text{L}$. A sample size of 10 per group will provide 81% power to detect a 22.8% and 51.8% difference in bound and pore water at an α of 0.05. Note that these changes are typically associated with a significant decrease in bone strength by destructive testing (18, 22). With 20 per group we can include a covariate in the regression models.

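### Type 2 diabetes, which the protocol itself links to fracture risk and to lower BMS, is neither excluded nor in the analysis, although the exclusions are said to remove such confounders

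*Protocol*

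**What the plan says.** **Eligibility (protocol 4.0).** Each of the three arms lists "Patients who have Type 1 diabetes" as an exclusion. No list names type 2 diabetes, and it is not among the examples given for other bone disease. After each list the protocol explains exclusions 1-5: "These exclusion criteria eliminate confounding factors that affect fracture resistance of bone in ways that are independent of osteoporosis".

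**Background (1.0 and 2.0).** Section 1.0 reports a higher-than-expected risk of hip fracture in people with type 2 diabetes. Section 2.0 says that "the age-related and diabetes-related increase in fracture risk is independent of" a person's aBMD. It also says that BMS "was found to be lower in post-menopausal women with type 2 diabetes than age-matched women without diabetes". Section 1.0 gives the site of that finding: the "bone measurement from OsteoProbe at the tibia mid-shaft was found to be different between women with and without type 2 diabetes".

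**Analysis (10.0).** Groups are first compared by Mann-Whitney test. General linear models then test fracture type "after adjusting for aBMD (or T-score), BMI, and age". The 60 operative patients are justified as 15 per variable with three covariates. Section 4.0 states that nothing is randomized. Nothing in the protocol is stratified, matched or analysed by type 2 diabetes.

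**The concern.** By the protocol's own account, type 2 diabetes is related to both sides of the Aim 1 comparison: to fracture, and to the quantity measured. It therefore fits the stated reason for exclusions 1-5, yet it is left in and does not enter the analysis.

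The low-energy and high-energy groups are formed by how the fracture happened, so nothing balances diabetes between them. If the low-energy group holds more type 2 diabetics, a lower BMS there could be read as a sign of osteoporotic bone when diabetes accounts for part of it. As planned, the results would give no means of telling. The rationale in 4.0 would also lead a reader to think that the question had been closed by design.

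**Working it through.** **1. The plan's own figures.**
- Covariate sizing: 60 / (1 fracture type + 3 covariates) = 60/4 = 15 per variable. This reproduces.
- Power: 87% for an 11.2% difference with 15 per group, two-sided 5%. The SD is not printed, so the figure can only be solved backwards. A noncentral t calculation gives a standardized difference of 1.17, so SD = 11.2/1.17 ≈ 9.6% of mean BMS. The normal approximation gives 9.9%. The figure is plausible but cannot be verified.

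**2. Does the text make type 2 diabetes a candidate confounder?**

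| Link | What the protocol supports |
|---|---|
| Type 2 diabetes and fracture | Higher hip fracture risk (1.0); diabetes-related fracture risk independent of aBMD (2.0) |
| Type 2 diabetes and BMS | Lower in post-menopausal women with the disease than in age-matched women without it (2.0); measured at the tibia mid-shaft (1.0) |
| Tibia BMS and distal radius BMS | No correlation, p=0.19, 10 cadavers (3.0) |
| Type 2 diabetes and fracture group | Not reported |
| Removed by design | No: only type 1 is excluded (4.0) |
| Removed by analysis | No diabetes term (10.0); age, BMI and aBMD may act as partial stand-ins in the model |

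**3. Possible size.** The protocol gives neither the BMS deficit nor the prevalence by group, so both are assumptions.

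Bias in the unadjusted difference = BMS deficit × (prevalence in low-energy − prevalence in high-energy)

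- Low case: 5% × (0.30 − 0.10) = 1.0% of BMS; 1.0/11.2 = 9% of the target.
- High case: 11% × (0.30 − 0.05) = 2.75% of BMS; 2.75/11.2 = 25% of the target.

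The standard error of the difference with 30 per group is 9.6 × √(2/30) = 2.48% of BMS, so these biases are 1.0/2.48 = 0.40 and 2.75/2.48 = 1.11 standard errors. With no other difference between the groups, a two-sample t-test would give p<0.05 in 6.8% and 19.4% of trials, against a nominal 5%.

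**4. How far this depends on the assumptions.** A wider grid (deficit 5-15%, gap 10-40 points) gives 0.5% to 6.0% of BMS, or 4% to 54% of the target, with rejection rates from 5.5% to 66%. The range in step 3 is therefore an illustration, not a bound. Nowhere in the grid does diabetes produce the full 11.2%. If diabetes were commoner in the high-energy group, the bias would run the other way.

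**5. Adjusted model.** No figure can be given. It would need the diabetes imbalance that remains at given age, BMI and aBMD, and the protocol has no data on that.

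**The case against.** There is a serious case on the other side, and much of it stands.

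- **Independence of aBMD.** A reader might infer from section 2.0 that adjusting for aBMD and age cannot remove a diabetes effect on BMS. The text does not support this. It calls the diabetes-related *fracture risk* independent of aBMD. For BMS it reports only a comparison with age-matched women, and it says nothing about BMI.
- **Age as the source of imbalance.** If type 2 diabetes is commoner in the low-energy group mainly because that group is older, age in the model may absorb much of the imbalance. It absorbs none in the Mann-Whitney test.
- **Site and population.** The BMS finding is from the tibia in post-menopausal women. The trial indents the distal radius in adults of both sexes. Saying that type 2 diabetes lowers the Aim 1 outcome would go too far. Equally, ten cadavers aged 78 to 98 are weak evidence that no relation exists.
- **Volunteers.** A reader might extend the point to the volunteer comparisons. Volunteers are not indented (section 6.0), so there is no BMS comparison with them, and the protocol reports no diabetes effect on bound or pore water.
- **Diabetes as signal.** Section 1.0 wants a tool that reflects how ageing and diabetes weaken bone. Diabetes may be one route to a fragility fracture, and a diabetes term in the main model could then remove part of what the study is looking for. This argues against making the term mandatory in the main model. It does not argue against recording diabetes, and the protocol nowhere says that type 2 diabetes is retained on purpose.
- **An unseen SAP.** It might add a sensitivity analysis. The protocol nevertheless fixes three covariates, sizes the study on them and states the rationale for the exclusions.

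**Conclusion.** The inconsistency is in the text: section 4.0 says such confounders are eliminated, while a factor that sections 1.0 and 2.0 describe in those terms remains in all arms and outside the analysis. The consequence is conditional. Part of a BMS difference could reflect type 2 diabetes if it is commoner in the low-energy group and if the tibia finding carries over to the distal radius.

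Under the assumed 5-11% deficit and 20-25 point gap, the unadjusted bias is about 1.0-2.75% of BMS, or 9-25% of the 11.2% target. The bias in the adjusted model may be smaller and cannot be computed from the protocol. The documents do not support the stronger conclusions that the three covariates must fail or that the planned model is invalid. The point deserves action because the check costs little and, without it, the result cannot be separated from a confounder that the protocol itself describes.

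**What to change.** 1. Keep eligibility and the three-covariate model as the main analysis.
2. Record type 2 diabetes (yes/no) from the medical records already reviewed for eligibility (section 5.0), and report it by fracture group.
3. Add two sensitivity analyses for BMS: the fracture-type comparison with a type 2 diabetes term, and the same comparison without type 2 diabetics. If the difference does not persist, do not attribute it to osteoporotic bone alone.
4. The same check for bound and pore water is optional. For volunteers, who are screened by phone, it would need one added question.
5. Reword the rationale after each exclusion list in 4.0 so that it no longer implies that all such factors have been eliminated, and state that type 2 diabetes is retained and examined in the analysis.

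**Cost.** One chart variable, and 60/5 = 12 rather than 15 participants per variable in the sensitivity model (keeping 15 would take 5 × 15 = 75 patients). The diabetes term will be imprecise if few diabetics enrol. At the assumed prevalences there would be about 0.30 × 30 = 9 in the low-energy group and 0.05 × 30 to 0.10 × 30, or 1.5 to 3, in the high-energy group. A difference that weakens in these analyses should therefore be read with its confidence interval, not by its p-value alone.
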